5.5 Treatment misallocation

If patients were randomized but not treated, the patients will appear on the study flowchart as randomized but not treated. This is the extent of how much the patient will be reported.

5.6 Protocol deviation

The following sections describe any protocol deviations that relate to the statistical analyses and forms the requirements for exclusion from the PPS.

5.6.1 Deviations to inclusion and/or exclusion criteria

Any patient who enters the study when the inclusion or exclusion criteria would have prevented entry, will be considered to have had a protocol deviation.

5.6.2 Deviations assessed post-randomization

Any patient who withdraw their consent during the observation period of 48 hours following administration of study medicine.

Randomised patients that for any medical reason will be prevented from completing the study according to study protocol.

6.0 ASSESSMENT, DEFINITION AND DERIVED VARIABLES

6.1 Primary outcome: High sensitive troponin I

Level of troponin I is measured at baseline (before administration of test drug) and at fixed time points following administration of test drug, and is a continuous variable measured in ng/L.

6.1.1 CMT pilot trial

Level of troponin I is measured at baseline and at 4, 10, 24 and if necessary 48 hours after study drug administration.

6.1.2 CMT2 trial

Level of troponin I is measured at baseline and at an interval of 6-10 hours after study drug administration.

6.2 Secondary outcomes

6.2.1 Other myocardial biomarkers.

The following myocardial biomarkers will be analysed at the same time points in the CMT pilot trial.

- Troponin T, a continuous variable measured in ng/L. The lower detection level of troponin T is 5 ng/L.
- CK, a continuous variable measured in U/L.
- CK-MB, a continuous variable measured in µg/L. The lower detection level of CK-MB is 1 µg/L.
- NT-proBNP, a continuous variable measured in ng/L. The lower detection level of NT-proBNP is 50 ng/L.

All measurements of biomarkers below their detection limits will be randomly imputed from a uniform distribution with lower limit equal to 0 and upper limit equal to the detection limit.

6.2.2 Other blood analyses

The following analyses will be performed at the same time points as for analysis of troponin I, for the CMT pilot trial at 0, 4, 10 and 24 hours and for the CMT2 trial at 0 and 6-10 hours after study drug administration.

- Hemoglobin, a continuous variable measured in g/100ml.
- Sodium (Na), a continuous variable measured in mmol/L
- Biobank analyses, continuous variables measured in units according to the specific variable.

6.2.3 Uterine tone

Uterine tone will be evaluated by obstetrician in charge of the C-section at 2.5 and 5 minutes after test drug administration

A numeric rating scale ranging from 0-10 is used (0 = no effect, 7 = clinically satisfactory contraction, 10 = maximal uterus contraction). The variable will be treated as continuous in the statistical analyses.

In case of need for additional uterotonic agent(s) for adequate uterine tone, time to rescue medication will be reported as a continuous variable in minutes.

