4.2 Statistical decision rule

The primary and all secondary outcomes will be analysed with two-sided tests and confidence intervals and a statistical significance level of 5%.

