6.3 Summary of endpoints (TABLE)

OUTCOME	ENDPOINT	TYPE
Primary	Troponin I level	Continuous
Other myocardial markers	Troponin T level	Continuous
	CK level	Continuous
	CK-MB level	Continuous
	NT-proBNP level	Continuous
Other blood analyses	Hemoglobin level	Continuous
	Sodium level	Continuous
	Biobank analyses	Continuous
Uterine tone	Uterine tone	Continuous
	Time till rescue, min	Continuous
Blood loss	Calculated blood loss, ml	Continuous
Perioperative side effects	Severity of side effects	Ordered categorical
	Treatment of side effects	Binary
Postoperative pain and side eff.	Pain at rest	Continuous
	Pain after coughing	Continuous
	Nausea	Continuous
	Tiredness	Continuous
Consumption of analgetics	Morphine consumption, mg	Continuous
QOL forms	Modified three simple questions	Continuous
	PCS	Continuous
	PCS \geq 30	Binary
	HSCL-25	Continuous
	HSCL-25 \geq 1.75	Binary
ECG changes	Occurrence ischemic episode	Binary
	Duration ischemic episode, sec	Continuous
	ST-segment depression, mV	Continuous
	Prolonged QTc interval	Binary
	Beat to beat analyses QTc interval	Continuous
	Occurrence of arrhythmia	Binary
Time consumption	Time consumption, min	Continuous

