7.4 Statistical methods

7.4.1 Primary and secondary analyses

The primary analysis will be a modified intention to treat analysis of the primary outcome (highly sensitive troponin I) on the full analysis set. We will initially perform a blinded analysis of the primary outcome.

Secondary analyses will be:

1. A per protocol analysis on the primary outcome (troponin I) on the per protocol analysis set
2. Modified intention to treat analyses of all secondary outcomes on the full analysis set
3. Sensitivity analyses to examine the impact of missing data (Section 7.4.5)

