7.4.3 Continuous outcomes measured at single time points

Continuous outcome variables measured at single time points will be analysed with two-sample t-tests (and 95% confidence intervals for the differences between means), with adjustment for unequal variances (the Welch U test). In situations where the distribution of the variable is difficult to assess or deemed to be highly skewed, median regression models will be used instead of t-tests to test and estimate differences in medians.

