7.4.5 Handling of missing data

Due to a short interval of observation in the CMT trial, only 48 hours after test drug administration, we expect a low level of missing data in this trial.

For categorical outcomes and continuous outcomes measured at one or two timepoints, a complete case analysis will be the primary analysis. In addition, sensitivity analyses will be

performed for the primary outcome, where missing data will be imputed according to the following scenarios:

1. Best-case outcome in the oxytocin group and worst-case outcome in the carbetocin group.
2. Worst-case outcome in the oxytocin group and best-case outcome in the carbetocin group.

Best case outcome = group mean + 2SD

Worst case outcome = group mean - 2SD, levels below 0 are set to 0.

3. Group-specific mean values

Similar sensitivity analyses for missing data will be performed for other continuous and categorical secondary end points, if the proportion of missing outcome values is greater than 10%. Best and worst case for categorical variables will be the lowest or highest possible score according to each variable. For the binary variable occurrence of arrhythmia, for instance, best case score = 0 (no episodes of arrhythmia) and worst case score = 1 (one/more episodes of arrhythmia).

Continuous variables measured at more than two time points will be analysed with linear mixed models (Section 7.4.2), which automatically handle missing data under the missing at random assumption.

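### Time to rescue uterotonic exists only for rescued women, no endpoint records whether rescue was given, and the only SAP method that fits compares a subset selected after randomisation

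*SAP*

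**What the plan says.** SAP 6.2.3 creates the variable conditionally: "In case of need for additional uterotonic agent(s) for adequate uterine tone", the "time to rescue medication will be reported as a continuous variable in minutes". Table 6.3 carries it under uterine tone as "Time till rescue, min", type continuous. Neither place has a yes/no variable for rescue, a value for women never rescued, or a censoring rule.

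No method is named for this variable, so it falls under the general rules:

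- SAP 4.2: "The primary and all secondary outcomes will be analysed with two-sided tests and confidence intervals and a statistical significance level of 5" per cent.
- SAP 7.4.1: "Modified intention to treat analyses of all secondary outcomes on the full analysis set".
- SAP 7.4.3: "Continuous outcome variables measured at single time points will be analysed with two-sample t-tests", with a Welch adjustment; where the distribution is highly skewed or hard to assess, "median regression models will be used instead of t-tests to test and estimate differences in medians".
- SAP 7.4.5: "For categorical outcomes and continuous outcomes measured at one or two timepoints, a complete case analysis will be the primary analysis".

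Elsewhere the SAP does supply the binary half of such a pair. Ischaemic episodes have an occurrence variable beside their duration (6.2.9), and treatment of side effects is coded 0/1 (6.2.5). Protocol 5.5 has all medication registered with dose and time, and protocol 6.2.2 continues this to 48 h.

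**The concern.** Needing an additional uterotonic happens after randomisation and may itself be affected by the study drug. Women who have a rescue time in one arm are therefore not comparable, by design, with those who have one in the other. A comparison of times in that subset is not the full-analysis-set comparison that 7.4.1 asks for, and it does not answer the natural question of how many women in each arm needed more drug.

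At stake is how one secondary variable is read. A drug that halves the need for rescue could show no difference in time to rescue. It could also appear to bring rescue forward or delay it, depending only on which rescues it prevented. The proportion rescued can be derived from the registered data, but without prespecification it would be a post hoc analysis.

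**Working it through.** **The plan's own figure.** The documents give no figure for rescue rate or rescue time. The only related number is the sample size for troponin I in SAP 7.1.2: difference 1.37, SDs 0.79 and 4.48, two-sided 5%, 80% power. Welch power from the noncentral t is 0.798 at 88 per group and 0.803 at 89, so 178 is reproduced. It is used here only as a second arm size.

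**Which method applies.** The variable has no baseline value, so 7.4.2 does not fit. It is not categorical, so 7.4.4 does not fit. It is not measured at more than two time points, so the mixed models mentioned in 7.4.5 do not fit. That leaves 7.4.3, and complete cases under 7.4.5 means rescued women only.

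**Assumptions for the size.** 240 women as 120 per arm, with 89 per arm as the smaller case because SAP 5.2 expects some women to leave before receiving study drug; rescue rate halved in one arm; higher rate from 40% down to 6%. Women left out = 240 − 120(p1 + p2); for 30 vs 15% this is 240 − 120 × 0.45 = 186.

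Mid-P power is exact: sum Binomial(x; n, p1) × Binomial(y; n, p2) over all pairs (x, y) for which the doubled one-sided mid-P is below 0.05. The Welch column comes from 20,000 simulated trials per row, with rescue times from a constant hazard cut off at a fixed window, so that timing among rescued women is nearly the same in both arms.

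| Assumed rates | Expected rescued (120 per arm) | Left out of 240 | Welch, rescued only: rejects | Mid-P on any rescue, 120 per arm | Mid-P, 89 per arm |
|---|---|---|---|---|---|
| 40 vs 20% | 48 vs 24 | 168 (70%) | 6% | 93% | 83% |
| 30 vs 15% | 36 vs 18 | 186 (77.5%) | 5% | 80% | 67% |
| 20 vs 10% | 24 vs 12 | 204 (85%) | 5–6% | 58% | 46% |
| 10 vs 5% | 12 vs 6 | 222 (92.5%) | 6% | 29% | 23% |
| 6 vs 3% | 7.2 vs 3.6 | 229.2 (95.5%) | 7% | 17% | 13% |

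The median-regression fallback, with a bootstrap standard error from 100 replications, rejects in 7, 7, 7, 10 and 10% of trials down the same rows.

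**When the subset test cannot be run.** An arm has fewer than 2 rescues with probability (1−p)^n + np(1−p)^(n−1). At n = 120 this is 0.122 for p = 3% and 0.005 for p = 6%. The chance that at least one arm fails is 1 − 0.878 × 0.995 ≈ 13%. At 89 per arm it is 27%.

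**When timing differs.** Suppose 30% of control women are rescued, half early (mean 3 min) and half late (mean 10 min). Their mean rescue time is (15×3 + 15×10)/30 = 6.5 min. Now let the other drug reduce rescue to 18% in one of two ways:

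- Mainly late rescues prevented (15% early, 3% late): mean (45 + 30)/18 = 4.17 min, so the drug with fewer rescues looks 2.3 min faster to rescue.
- Mainly early rescues prevented (3% early, 15% late): mean (9 + 150)/18 = 8.83 min, so it looks 2.3 min slower.

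In 4,000 simulated trials the Welch test rejects in about 64% and 51% respectively at 120 per arm, and in 54% and 38% at 89. The benefit in rescue rate is the same in both cases, but the sign is opposite.

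**What the binary endpoint gives.** For 24 vs 12 of 120, the Wilson limits are 0.138–0.280 and 0.058–0.167. The Newcombe lower limit is 0.10 − √[(0.200−0.138)² + (0.167−0.100)²] = 0.009. The upper limit is 0.10 + √[(0.280−0.200)² + (0.100−0.058)²] = 0.191. The interval is 0.9 to 19.1 points. For 12 vs 6 of 120 it is −1.9 to 12.2 points.

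**The case against.** The best defence is the verb. In 6.2.3 uterine tone is to be treated as continuous in the analyses, whereas rescue time is only to be reported. Read that way, the SAP plans a description of rescued women, which is close to what is recommended below. This stands as a possible reading, so it would go too far to infer that the SAP commits itself to a flawed test. But 4.2 and 7.4.1 exempt no secondary outcome, table 6.3 lists this one, and 6.2.8.2 and 6.2.8.3 use the same verb for variables listed as endpoints in that table. The intention has to be stated.

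A reader might also infer that 7.4.5 would impute rescue times for women who needed none, since the share without a time exceeds 10% unless at least 90% are rescued. The documents do not support this: nothing codes no rescue as a missing value. It is a reason to add one clarifying sentence and no more.

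Nor does the 5–7% rejection rate hold for every pattern of rescue times. It follows from giving both arms nearly the same timing among rescued women, and it fails when the drugs prevent different kinds of rescue.

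It is also fair that rescue rate is neither a protocol secondary endpoint nor an SAP objective, that tone and calculated blood loss are still compared in treated women whether or not they were rescued, and that the proposed test has little power at low rates. These points limit the weight of the concern but do not remove it.

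**Conclusion.** The gap is real and of limited size. A listed secondary endpoint is defined only for rescued women, the event that defines the subset has no endpoint of its own, and the SAP's general rules lead to a comparison within that subset. Depending on the timing of rescues, the comparison either carries no information about the rescue rate or gives a difference whose sign reflects which rescues were prevented.

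That conclusion follows from the text. The sizes rest on assumed rescue rates, a halving of the rate, and assumed times, because the documents give none of these. At 10 vs 5% or below, the gain from a binary endpoint is an interpretable estimate and interval rather than power. The troponin I analysis and the sample size are unaffected. The change should be made because it costs little and replaces a comparison that can mislead.

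**What to change.** - Add to table 6.3 a binary secondary endpoint, *additional uterotonic given (yes/no)*, within a stated time window after study drug. Analyse it in the full analysis set with the Fisher mid-P test and Newcombe interval of 7.4.4.
- State in 6.2.3 that no rescue is an outcome coded 0 and not a missing value, so the imputation rules in 7.4.5 do not apply to it.
- State that time to rescue is given descriptively among rescued women, with the number rescued per arm.
- If a test of time is wanted, use a time-to-event method such as Kaplan–Meier with a log-rank test, with women not rescued censored at the end of that same window. End of surgery is not a suitable censoring point, because surgery time is itself an SAP outcome and may depend on atony. On the assumed rates above, the log-rank test with fixed-window censoring has power of 93, 80, 59, 31 and 19% at 120 per arm, so nothing is lost against the binary test.

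The cost is one table row and about three sentences. No new data are needed, since medication is already registered with dose and time. A table of agents by arm is optional. No change to the rescue rule is proposed.

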6.2.4 Blood loss

Blood loss will be estimated by the formula for calculated blood loss as published by Stafford, revised with weight in kg and height in cm(7).

A continuous variable measured in mL.

6.2.5 Perioperative side effects.

During the first 10 minutes after administration of test drug, the patient will be asked to report any side effects. Severity of side effects will be registered in time gaps as follows 0-2 min, 2-5 min and 5-10 min.

Severity of side effects is an ordered categorical variable:

- 0 = no side effects at the given point
- 1 = mild side effects
- 2 = moderate side effects
- 3 = severe side effects.

Treatment given to alleviate side effects (a binary variable) will be registered as

- 0 = no treatment administered
- 1 = treatment administered

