6.2.2 During Treatment

Vital signs, preoperative pain status, and baseline blood samples will be registered before anesthesia. Spinal anesthesia will be given according to departmental procedure. During surgery, the patient will be supine with a left lateral tilt (operating table tilt, or operating wedge under her right hip). Hypotension (systolic arterial pressure <90 mmHg) is treated with an extra i.v. bolus of phenylephrine if the heart rate is above 60 beats/min or with i.v. ephedrine 5–10 mg if 60 beats/min or below. The level of anesthesia will be tested by cold sensation 5 min after spinal anesthesia as well as by pinching with surgical tweezers before horizontal skin incision (Pfannenstiel). The study drug will be injected slowly, over the course of 60 s, starting when the baby's head and shoulders are delivered. Exteriorization of the uterus is performed routinely according to departmental policy. The patient will be asked if she experienced any of the listed side effects, and to grade the intensity of the side effects as mild, moderate, or severe. The duration of the side effects will also be recorded. Side effects, pain intensity and medications will be registered until 48h. Registration of side effects will be performed at the following intervals, 0–2 minutes, 2–5 minutes and 5–10 minutes after study drug administration. The rest of the observation period side effects will be registered when reported by the patient.

The obstetrician in charge of the Cesarean delivery assess uterine tone 2.5, and 5 min after administration of study drug, using a numeric rating scale that range from 0 to 10, where a score of 0 means "no effect", 10 means "maximal uterus contraction", and 7 indicates "clinically satisfactory contraction". This uterine contraction scale was introduced to the obstetricians earlier in a previously published RCT. Because visual assessment of blood loss during delivery is of limited value, we will calculate estimated blood loss using the formula for calculated estimated blood loss as published by Stafford(5), revised with weight in kg (last measurement prior to operation), height in cm.(1)

Routine assessments of newborn status are registered (Apgar 1 and 5 minutes, umbilical vein and artery acid-base status).

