8.2 Expected Adverse Events

Expected side effects are feeling of warmth, chest pain, shortness of breath, palpitations, flushing, headache, nasal congestion, xerostomia, and metallic taste or other events or reactions listed in the SmPCs of the investigational medicinal products. Both drugs in the study will lead to vasodilatation with decrease in blood pressure and increasing heart rate.

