7.1.2 CMT2 trial

Based on preliminary results of the CMT pilot trial, the largest difference in plasma troponin I concentration was found at 10 hours, with a mean±standard deviation change from baseline of 0.41 ± 0.79 ng/L in the carbetocin group versus a mean change of 1.78 ± 4.48 in the oxytocin group. The sample size calculation was based on 80% power to detect a between-group difference in change from baseline to 10 hours of 1.37, to be analysed using a two-sample T-test with adjustments for unequal variances. With a significance level of 5%, we will need to include 178 patients (89 in each treatment group) in the CMT2 trial. To adjust for loss of information from missing values and patient drop outs, 240 women will be enrolled. The drop-out rate after enrolment is expected to be low as the duration of the study is short.

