7.4.4 Categorical outcomes

Binary outcomes will be analysed with Fisher mid-P tests and Newcombe hybrid score confidence intervals for the difference between probabilities.

Ordered categorical outcomes will be analysed with score tests for effect in a proportional odds model (the Wilcoxon-Mann-Whitney test).

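### No prespecified comparison in the SAP separates chest pain, shortness of breath and palpitations from the other early side effects, and the 0-3 severity score would probably not detect an excess of them

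*SAP*

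**What the plan says.** **Collection.** Protocol 8.2 names nine effects: "Expected side effects are feeling of warmth, chest pain, shortness of breath, palpitations, flushing, headache, nasal congestion, xerostomia, and metallic taste". It adds that both drugs cause vasodilatation, with a fall in blood pressure and a rise in heart rate. Protocol 6.2.2 has the woman prompted against a list: "The patient will be asked if she experienced any of the listed side effects, and to grade the intensity of the side effects". This is done for 0-2, 2-5 and 5-10 minutes after study drug.

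**Analysis variables.** SAP 6.2.5 keeps the three windows and states: "Severity of side effects is an ordered categorical variable". Code 0 stands for having no side effects at that point; codes 1 to 3 are mild, moderate and severe. A second variable records whether treatment was given. Table 6.3 has one row for "Severity of side effects" and one for treatment. Neither names a symptom.

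**Tests.** SAP 7.4.4: "Ordered categorical outcomes will be analysed with score tests for effect in a proportional odds model", that is, the Wilcoxon-Mann-Whitney test. Binary outcomes get a Fisher mid-P test and a Newcombe interval. SAP 4.2 applies "two-sided tests and confidence intervals and a statistical significance level of 5" per cent to all outcomes.

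**Other commitments.** Protocol 8.4 has the nature of each adverse event entered in the CRF. Protocol 10.3 promises description of all adverse events by type and severity, and an analysis of group differences in side effects whatever the primary result. The SAP has no adverse-event section that carries this forward.

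**The concern.** The trial asks whether one drug is harder on the heart than the other. In CMT2 there is little cardiac information beyond troponin I at 6-10 hours. SAP 2.3 restricts the analysis of ECG changes to the pilot, and SAP 6.2.1 places troponin T, CK, CK-MB and NT-proBNP there too. The early symptoms are the only patient-reported cardiac signal among the SAP's endpoints.

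If one grade covers all symptoms, mild chest pain and mild metallic taste both score 1, and mild chest pain in a woman with moderate flushing changes nothing. Vasodilator symptoms may be common in both arms and would then dominate the score. The planned test could show no difference while chest symptoms differ. A cardiac contrast chosen after unblinding would be open to a charge of selective reporting.

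**Working it through.** **1. Is the score pooled?** The SAP does not say how several symptoms become one grade. Two features point to pooling. Code 0 is defined by the absence of any side effect at that time. And table 6.3 lists separate items where separate items are meant: pain at rest, pain after coughing, nausea and tiredness each have a row, while perioperative severity has one. If the scale were instead applied per symptom, there would be 9 symptoms × 3 windows = 27 comparisons, with none singled out as cardiac. On either reading, no cardiac-symptom comparison is prespecified.

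**2. Arm sizes.** SAP 7.1.2 sizes the trial on troponin only, for "80% power to detect a between-group difference in change from baseline to 10 hours of 1.37", using "0.41 ± 0.79 ng/L in the carbetocin group versus a mean change of 1.78 ± 4.48 in the oxytocin group".
- Variance sum: 0.79² + 4.48² = 0.6241 + 20.0704 = 20.6945.
- Normal formula: (1.960 + 0.842)² × 20.6945 / 1.37² = 86.5, so 87 per arm.
- Welch t-test (noncentral t, Satterthwaite degrees of freedom): 79.8% power at 88 per arm and 80.3% at 89.

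The stated 89 per arm (178 in all) is reproduced. I use 89 per arm, and 120 per arm (240/2) as the upper end.

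**3. Assumptions, none of them in the documents.**
- The score is the worst grade over all symptoms, one value per woman.
- Non-cardiac effects have the same distribution in both arms and are independent of cardiac symptoms.
- 20%, 40% or 60% of women have no non-cardiac effect. The middle case is 40/40/17/3% none/mild/moderate/severe; the others keep the 40:17:3 split.
- Cardiac symptoms occur in 5% v 15% or 10% v 25%.

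**4. How the signal is diluted.** With independence, P(worst ≤ k) = P(non-cardiac ≤ k) × P(cardiac ≤ k). Take the middle background, cardiac symptoms 5% v 15%, 70% of them mild and 30% moderate:
- P(0): 0.40 × 0.95 = 0.380 v 0.40 × 0.85 = 0.340.
- P(≤1): 0.80 × (0.95 + 0.035) = 0.788 v 0.80 × (0.85 + 0.105) = 0.764.
- P(≤2): 0.97 in both arms.

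The scores are therefore 38.0/40.8/18.2/3.0% v 34.0/42.4/20.6/3.0%. A 10-point difference in cardiac symptoms becomes a 4-point difference in the proportion with no side effects.

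**5. Power, two-sided 5%.** The pooled score is tested by tie-corrected Wilcoxon-Mann-Whitney (20,000 simulated trials per setting). The binary endpoint is tested by Fisher mid-P (exact calculation). Pooled ranges are over the three backgrounds.

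| Cardiac symptoms | Per arm | Binary endpoint | Pooled, cardiac 70% mild / 30% moderate | Pooled, cardiac all severe |
|---|---|---|---|---|
| 5% v 15% | 89 | 61% | 7-12% | 22-24% |
| 5% v 15% | 120 | 74% | 7-15% | 28-30% |
| 10% v 25% | 89 | 76% | 9-22% | 42-45% |
| 10% v 25% | 120 | 87% | 10-28% | 53-57% |

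Making every cardiac symptom mild lowers the floor to 5-6%. Hence roughly 6-57% for the pooled score against roughly 60-88% for the binary endpoint.

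**6. A wider grid.** A second set crossed five rate pairs (2% v 10% up to 10% v 30%), four backgrounds (20-80% of women with a non-cardiac effect) and four severity mixes: 80 scenarios per arm size. The pooled score had under 50% power in 74 of 80 at 89 per arm and 68 of 80 at 120. The binary endpoint had 61-93% and 74-98%. The best pooled results, 73% and 84%, came from 10% v 30% with a light background and mostly severe cardiac symptoms.

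**The case against.** **Pooling is not written.** This stands as a limit. The SAP text would allow the scale to be applied per symptom, and a worst-grade rule appears nowhere. The power figures hold only if the score is pooled in that way.

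**A reader might infer that symptom type is lost and an excess would go unseen.** The documents do not support that. Women are asked about listed effects, the nature of events goes in the CRF, and Protocol 10.3 promises description by nature. Counts by type could show an imbalance. What is missing is a prespecified comparison with an estimate and interval.

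**A reader might infer that the severity score is the only side-effect outcome tested.** It is not: treatment of side effects is a binary secondary outcome and gets its own Fisher mid-P test. It does not identify symptoms either.

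**A reader might infer that power is always very low.** It need not be. Fixing cardiac symptoms at mild or moderate favours masking; with severe symptoms or a light background the pooled test does much better, though it stayed below the binary endpoint in every setting run.

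**The cardiac grouping is the review's own.** The documents do not class the three symptoms together, and palpitations may reflect vasodilatation, which would dilute a composite too. That is a reason to show each symptom separately as well.

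**It is an unpowered secondary outcome, and troponin I carries the cardiac question.** True, and the primary analysis is not affected. It does not explain why the SAP's side-effect tests should ignore symptom type in a cardiotoxicity trial.

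**Conclusion.** The point holds as a gap in the prespecified analysis. Under SAP 6.2.5 and 6.3 no planned comparison separates chest pain, shortness of breath or palpitations from vasodilator symptoms, and the rule for turning several symptoms into one grade is missing. If the score is the worst grade over all symptoms, its test would probably miss a moderate cardiac-symptom excess: roughly 6-57% power against roughly 60-88% for a binary endpoint at 89-120 per arm. The gap in prespecification is plain from the text. Its size rests on the pooling reading, the assumed rates and severities, and independence of cardiac and non-cardiac symptoms. The change is worth making before unblinding.

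**What to change.** - In SAP 6.2.5, state how several symptoms become one severity score, and how the three windows are used.
- Add to SAP 6.2.5 and table 6.3 one binary secondary endpoint: any chest pain, shortness of breath or palpitations within 0-10 minutes of study drug. Analyse it on the full analysis set with the Fisher mid-P test and Newcombe interval of SAP 7.4.4.
- Tabulate each of the three symptoms separately by arm and worst grade.
- Keep the overall severity score as the tolerability measure.

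**Cost.** SAP wording and one table, from symptoms women are already asked about; no change to sample size or conduct. The downside is one more secondary comparison, to be reported as an estimate with its interval. A single composite limits multiplicity: with independent tests at 5%, three separate symptoms would give 1 − 0.95³ = 14% chance of at least one false positive, and three symptoms in three windows 1 − 0.95⁹ = 37%.
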